#### 9.6.5 Primary analysis

The primary analyses are based on a non-inferiority test of birth in water versus on land, comparing 1) the proportion of mothers that have OASIS, and 2)the proportion of babies with a composite outcome of 'adverse neonatal outcome or treatment'.

To test the primary hypothesis of non-inferiority between birth in water and on land, the two outcomes will be evaluated for non-inferiority using logistic regression models, in the first instance with no adjustment for covariates. Adjusting for potential confounders may result in a more precise treatment effect estimate. The potential confounders of both primary outcomes (listed in table 1) will be considered and the impact on bias through conditional associations when conditioning on these covariates will be assessed using directed acyclic graphs (DAGs). The main logistic model will incorporate these selected covariates through regression adjustment. Results will be reported as an (unadjusted) odds ratio (birth in water compared to on land), and a two-sided 90% confidence interval (CI) for the (unadjusted and adjusted) odds ratio will be calculated. Non-inferiority will be concluded if the upper limit of the 90% CI for the difference in neonatal outcome between the groups is less than 1.0% (OR<1.21). Similarly, for the mother's outcome, non-inferiority will be concluded if the upper limit of the 90% CI for the difference in the proportion of OASIS between the groups is less than 1.0% (OR<1.23) in nulliparous 'low-risk' women and less than 0.6% (OR<1.38) in parous 'low-risk' women. The data will then be combined to assess the effects averaged across both strata.

If non-inferiority is shown, then a superiority analysis will be conducted as a secondary analysis of the primary outcomes using logistic regression and will be presented as an (unadjusted and adjusted) odds ratio of outcomes in the waterbirth group compared with the birth on land group. Parameter estimates will be provided alongside 95% CI and p-value. Secondary outcomes will have non-inferiority testing as detailed above.

	Maternal	Adverse neonatal
	outcome: OASIS	composite outcome
Maternal age (years)	√	$\checkmark$
Maternal BMI	✓	
Parity	√	
Duration of labour	✓	
Gestational age at delivery (weeks)	√	$\checkmark$
Child birth weight (g)	✓	$\checkmark$
Child head circumference (cms)	√	
Maternal thyroid disease (including hypothyroidism)		$\checkmark$
Pre-labour ruptured membranes		$\checkmark$
Intrapartum fever		$\checkmark$
Fetal growth restriction		$\checkmark$
Child gender		$\checkmark$
Meconium stained liquor		$\checkmark$

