### 5.4 Secondary Outcomes

Secondary outcomes of parental, clinical and financial importance have been identified. Data relating to maternal or neonatal readmission to hospital within seven days of birth is already reported by community midwives and captured in EuroKing® systems at the point of discharge from midwifery care. Data relating to some primary and secondary outcomes are not currently captured in EuroKing® maternity information systems and at site opening the EuroKing® E3 systems at sites will be amended to prospectively collect these data.

Maternal secondary outcomes: Maternal Intrapartum: Shoulder dystocia and required management, management of the third stage of labour, need and reason for obstetric involvement in woman's care including sepsis; mode of birth, maternal position at birth, treatment for haemorrhage, incidence and management of perineal and other genital trauma. Maternal Postnatal: duration of postnatal stay, breast feeding initiation and continuation, higher level care, and maternal readmission to hospital within seven days of birth.

Infant secondary outcomes: Snapped umbilical cord prior to clamping, skin to skin contact at birth, timing of cord clamping, resuscitation, Apgar scores, administration and duration of intravenous antibiotics. Incidence of: lumbar puncture, culture proven infection, brachial plexus injury; treatment for jaundice; readmission to hospital within seven days of birth; therapeutic hypothermia;

TPL/003/2 v1.0

Page **15** of **38** 

neonatal unit admission and duration; cause of neonatal death; respiratory support. Where available, and where the risk status and pool usage of mothers can be determined, retrospective data will be used in addition to prospective data, to describe the occurrence of these infant outcomes.

Additional data items with accompanying background development required to fully answer the research aims will be added to E3 systems at study sites, and will include:

- Maternal risk factors at pool entry
- Maternal risk factors developing during labour
- Time of entry into pool
- Time of last leaving pool
- Reason for leaving pool if prior to birth
- Partial birth in water (breech / shoulder dystocia)
- Birth position in pool
- Conversion from planned physiological to active third stage labour management.
- Delivery of placenta in or out of water
- Treatment for haemorrhage
- Reason for obstetric involvement in woman's care

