### 7 Study design and setting

A natural experiment using a cohort design with a qualitative component will answer the study objectives by using a combination of data captured retrospectively and prospectively in electronic NHS maternity and neonatal information systems. The qualitative component will explore factors associated with high and low rates of pool use; data will be gathered in online discussion groups, focus groups and one-to-one interviews with key stakeholders, including mothers/to be.

To answer all research objectives approximately 600,000 individual computerised maternity records held on secure NHS servers at around 30 NHS sites, covering the period January 2015 – November 2020 will be accessed. To provide necessary denominator data, and to be able to compare characteristics of pool users and non-pool users, a minimal data set will be extracted relating to women who did not use a pool in labour, whilst a more extensive dataset will be extracted for women who did use a pool in labour. An important clinical question is whether there is a differential effect of waterbirth on severe perineal trauma (OASIS) amongst nulliparous and parous women. To undertake this subgroup analysis will require a necessarily large sample (30,000). As data relating to perineal trauma and waterbirth are already captured, and to avoid unnecessarily prolongation of the study, this analysis will use a combination of retrospective and prospectively collected data, including births from 2015 to 2020.

The sample required for the neonatal primary outcome is smaller (16,200) and, as all essential data are not currently collected for one component of this composite outcome (antibiotic administration within 48 hours of birth on postnatal wards) additional data fields will to be added to maternity systems at participating NHS sites. Therefore, we will collect these data on births prospectively during the period June 2018 to November 2020.

Some neonatal outcomes of interest, including neonatal hypoxia, respiratory support or neonatal mortality, are already held by study sites or by the National Neonatal Research Database (NNRD). Where available and where the risk status, and pool usage of mothers can be determined, retrospective data will be utilised to increase the power of the analysis around secondary neonatal outcomes.

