The NNRD holds individual patient level data on all babies admitted for National Health Service neonatal care in England, Scotland and Wales from 2014 to present. To obtain detailed treatment and outcome information on any baby who required admission to a neonatal unit, following their mother's pool use in labour, the identifiers of all babies born to women who used a pool during the period of prospective data collection will be extracted and matched to any records held by the NNRD.

The primary study aim is to compare maternal and neonatal outcomes for 'low risk' women who gave birth in water (Group 1) against 'low risk' women who left the water prior to birth for reasons other than clinical need (Group 2) Figure 1.

[figure not shown]

Figure 1 Study population groups

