#### 9.6.4 Inclusion in analysis

Women, and their babies, will be included in the study if the woman used water immersion at a study site during the period of data collection. For the purposes of providing denominator data and

Page 23 of 38

to fully answer the research objectives, a minimal data set will also be obtained on women at study sites who do not use water immersion.

To capture data relating to women who use any form of water immersion during labour 'use of a pool ' during labour, will pragmatically be being any women for whom water immersion analgesia is recorded in the EuroKing E3 system.

To capture births commenced in, but completed, out of water, such as in the event of shoulder dystocia or previously unrecognised breech presentation 'waterbirth' will be defined in the study as 'A birth in which the fetus is partially or totally expelled under water'.

Data relating to women and babies recorded in EuroKing as being 'Born Before Arrival' (BBA), or recorded as intentionally born without midwifery attendance, will be excluded from primary analysis.

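### The OASIS comparison sets no mode-of-birth condition, although waterbirth by definition excludes caesarean and in practice nearly all instrumental births, leaving a bias of unknown sign and size

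*Protocol*

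**What the plan says.** The maternal primary analysis (Protocol 9.6.5) is a "non-inferiority test of birth in water versus on land, comparing 1) the proportion of mothers that have OASIS". No mode of birth is named as a condition.

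- **Exposure.** Section 9.6.4 defines a waterbirth as "A birth in which the fetus is partially or totally expelled under water".
- **Exclusions.** The same section removes births before arrival and those "recorded as intentionally born without midwifery attendance, will be excluded from primary analysis". It excludes nothing by mode of birth.
- **Comparator.** Section 7 sets low-risk waterbirths against low-risk "women who left the water prior to birth for reasons other than clinical need (Group 2"). Section 9.6.5 speaks only of birth on land and does not repeat this limit.
- **Availability of the exit reason.** "Reason for leaving pool if prior to birth" stands in section 5.4 among the items to be added to the maternity system. For OASIS, section 7 says that "this analysis will use a combination of retrospective and prospectively collected data, including births from 2015 to 2020".
- **Adjustment.** "The main logistic model will incorporate these selected covariates through regression adjustment", chosen from Table 1. The OASIS candidates are maternal age, BMI, parity, duration of labour, gestational age, birth weight and head circumference.
- **Mode of birth** appears only as a secondary outcome ("mode of birth, maternal position at birth, treatment for haemorrhage", section 5.4). Section 9.6.5 says that secondary outcomes will be tested for non-inferiority in the same way.

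**The concern.** A caesarean cannot meet the waterbirth definition, and a forceps or ventouse birth hardly can. Any pool user whose labour ends that way can be counted only on the land side. Caesarean births carry almost no risk of OASIS, and instrumental births may carry a different risk from spontaneous ones. The two denominators therefore differ structurally in their exposure to the endpoint.

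The Group 2 limit conditions on why a woman left the pool, not on how her birth ended. A woman who leaves by choice and later has an instrumental birth remains in Group 2. For births before the new item was added, the protocol names no field from which Group 2 could be identified.

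The other planned analyses do not close the gap. The propensity score names age, parity and other characteristics, and the instrumental variable rests on unit culture. Entering mode as a covariate would not help either, because operative births have almost no counterpart in the water group.

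At stake is a safety conclusion. Instrumental births at raised risk lift the land rate and can let a harmful water effect pass. Caesareans lower the land rate and can make a harmless one fail. Separately, a non-inferiority test of mode of birth has its answer fixed by the exposure definition.

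**Working it through.** **Inputs from the protocol (9.6.1, 9.6.5).** OASIS 4.6% in nulliparous and 1.6% in parous women, given overall and not by mode; 7,500 per group in each parity stratum; margins 1.0 and 0.6 percentage points; 90% power; one-sided 5%; true difference zero.

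**The plan's own figures.** n per group = (1.645 + 1.282)² × 2p(1 − p) / margin².
- Nulliparous: 8.564 × 2 × 0.046 × 0.954 / 0.01² = 7,517.
- Parous: 8.564 × 2 × 0.016 × 0.984 / 0.006² = 7,491.
- Margin odds ratios: 5.6% against 4.6% gives 1.23; 2.2% against 1.6% gives 1.38.

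All agree with the protocol. The sample size is not in question.

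**Assumed inputs.** The documents give none of these, so they are varied: *p*, the OASIS rate in spontaneous vaginal births, set to 4.6% or 1.6%; *i* and *c*, the instrumental and caesarean shares of the land group; *k*, the OASIS risk ratio of instrumental to spontaneous birth. Caesareans are given zero OASIS risk.

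**Formulas.**
- Land rate = p(1 − i − c) + i·k·p, so the shift from the spontaneous rate is p[i(k − 1) − c].
- Chance of concluding non-inferiority = Φ[(margin − (w − l)) / SE − 1.645], with w and l the water and land rates and SE = √{[w(1 − w) + l(1 − l)] / 7,500}.

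**One row in full** (nulliparous, i = 10%, c = 5%, k = 2). Land rate = 4.6 × (0.85 + 0.20) = 4.83%. Put water exactly one margin above spontaneous land births, at 5.6%. The difference seen is 0.77 points and SE = 0.363 points. (1.00 − 0.77)/0.363 − 1.645 = −1.01, so Φ = 15.6%.

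| Stratum | i | c | k | Land rate | Shift (points) | Non-inferiority declared when water is one margin worse (nominal 5%) | Power when water equals spontaneous land births (nominal 90%) |
|---|---|---|---|---|---|---|---|
| Nulliparous | 0 | 0 | – | 4.60% | 0 | 5.0% | 89.9% |
| | 10% | 10% | 2 | 4.60% | 0 | 5.0% | 89.9% |
| | 10% | 5% | 2 | 4.83% | +0.23 | 15.6% | 97.2% |
| | 20% | 5% | 2 | 5.29% | +0.69 | 58.6% | 99.9% |
| | 20% | 5% | 3 | 6.21% | +1.61 | 99.4% | 100% |
| | 0 | 5% | – | 4.37% | −0.23 | 1.1% | 73.7% |
| | 0 | 10% | – | 4.14% | −0.46 | 0.2% | 48.9% |
| Parous | 0 | 0 | – | 1.60% | 0 | 5.0% | 90.0% |
| | 10% | 5% | 2 | 1.68% | +0.08 | 9.9% | 94.9% |
| | 20% | 5% | 2 | 1.84% | +0.24 | 27.4% | 99.0% |
| | 20% | 5% | 3 | 2.16% | +0.56 | 75.9% | 100% |
| | 0 | 5% | – | 1.52% | −0.08 | 2.2% | 82.2% |
| | 0 | 10% | – | 1.44% | −0.16 | 0.9% | 71.1% |

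**What a full-margin shift would need.** i(k − 1) − c must reach 1.0/4.6 = 0.217 (nulliparous) or 0.6/1.6 = 0.375 (parous).
- To hide a full margin with c = 5%, nulliparous: i = 26.7% at k = 2, or 13.4% at k = 3.
- To hide a full margin with c = 5%, parous: i = 42.5% at k = 2, or 21.3% at k = 3.
- To mimic a full margin with no instrumental births: c = 21.7% (nulliparous) or 37.5% (parous).

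**Cross-check with 4.6% taken as the whole comparator's rate.** Then p = 4.6/[(1 − i − c) + i·k].
- i = 15%, k = 2, c = 5%: p = 4.6/1.10 = 4.18%, so a true harm of 1.0 point shows as 0.58.
- i = 5%, k = 2, c = 15%: p = 4.6/0.90 = 5.11%, so no effect shows as a harm of 0.51.

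**The case against.** The strongest reply has four parts.

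**The comparator is already narrowed.** Section 7 does not compare waterbirth with every land birth. Leaving for a clinical problem is plausibly the main route to an operative birth, and Group 2 removes those women. This stands, and it rules out reading the comparator as all land births. It does not reach operative births after a non-clinical exit, and the exit reason is not shown to be available for retrospective births.

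**The size rests on assumptions.** This also stands. A reader might infer a bias as large as the margin in either direction. The documents give neither mode shares nor OASIS risk by mode, so they do not support that. Mimicking a full margin needs caesarean shares that look implausible in this group. Equal and opposite effects can cancel, as the 10%/10% row shows, and parous shifts are smaller relative to their margin.

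**Mode of birth may be a mediator.** The aim is to compare remaining in the pool with leaving it, so mode could be part of the effect, and restricting on it could introduce selection. This is weak under the protocol's own exposure definition. Exposure is settled only at expulsion, after any operative decision. Nor does the all-modes comparison mirror a stay-or-leave policy. A woman who means to stay but leaves for an operative birth has a clinical exit and falls outside both groups, while one who left by choice and has the same birth stays in Group 2. What remains is a reason to report both versions.

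**Not everything is visible.** Figure 1, on the population groups, could not be read, and the SAP is not at hand. But the protocol text itself fixes the exclusions, candidate covariates, margins and decision rule, and none of them mentions mode.

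**Conclusion.** The point holds as a structural imbalance that the plan leaves uncontrolled. Waterbirth excludes caesarean by definition. That it excludes nearly all instrumental births is a practical inference, since the definition also admits births begun in water and completed out of it. Neither the Group 2 limit, Table 1 nor the named sensitivity analyses deals with the operative births that remain on the land side.

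The direction and size of the bias cannot be established from the protocol. The calculations show only that modest mode shares would matter to the nulliparous decision, because the margin is narrow. The chance of wrongly declaring non-inferiority could be about three times nominal in a mild scenario and far higher in a stronger one, and a small caesarean share alone could cost about 16 points of power. These figures rest on assumed shares and risk ratios, on 4.6% and 1.6% holding for spontaneous births, and on 7,500 per group.

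The secondary-outcome point is smaller but clear: a water-versus-land non-inferiority test of mode of birth cannot be informative.

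**What to change.** 1. In 9.6.4 and 9.6.5, state that the comparator is Group 2, and say how it will be identified, or what will replace it, for births recorded before the exit reason was collected.
2. Prespecify the OASIS comparison among spontaneous vaginal births in both groups alongside the all-modes comparison. Name which is primary and why, and require any non-inferiority conclusion to be read against both.
3. Take mode of birth out of the water-versus-land non-inferiority tests and report it descriptively for all women who used a pool.

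**Cost.** Wording in the protocol and SAP and one further model run. Mode of birth is already a planned data item. The restricted analysis loses land births: if 10% to 20% of them were operative (assumed), keeping 7,500 per stratum needs 7,500/0.9 = 8,334 to 7,500/0.8 = 9,375. Section 9.6.1 expects nulliparous waterbirths to be the scarcest of the four groups, so this should be affordable. The restricted estimate also conditions on mode of birth, which is why the all-modes result should stay beside it.

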#### 9.6 Cohort Study Statistical considerations

#### 9.6.1 Sample size

The non-inferiority of birth in water compared to birth on land on rates of OASIS will be examined by parity. The Birthplace in England study found that overall 4.6% and 1.6% of nulliparous and parous women respectively, sustained OASIS. A sample size of 15,000 nulliparous and 15,000 parous 'low risk' women (7,500 each water and land) is required to obtain 90% power, and a 95% one-sided confidence interval around a treatment difference of zero. A non-inferiority margin of 1% or less,

Page **22** of **38** 

and 0.6% or less will be taken as clinically non-significant amongst nulliparous and parous 'low risk' women respectively. Since nulliparous women birthing in water are regarded as the least prevalent of the four groups, a data collection period providing data on 7,500 would ensure adequate numbers in the other three, more prevalent groups. These data will be combined to assess the effects averaged across both strata at an increased power, with a combined required sample size of 30,000 'low risk' women. We have assumed that 25% of the 6,600 waterbirths recorded in EuroKing® in 2015 were nulliparous women (1650/annum). Allowing for staggered site set-up, five years of combined retrospective and prospective data collection would be required (January 2015 – November 2020). The exact ratio of nulliparous and parous women who give birth in water will be determined once the retrospective data are examined, but with increasing numbers of waterbirths, with 18 of the 35 EuroKing® using sites, collectively undertaking 6,037 waterbirths in 2016, we are confident the study will have sufficient power to answer this important clinical question.

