For the neonatal primary outcome, an estimate of 5% is used for the proportion of babies born to 'low risk' mothers experiencing 'adverse neonatal outcome or treatment'. A non-inferiority margin of 1.0% or less will be taken as clinically non-significant. A sample size of 16,200 babies (8,100 per group water / land) are required to have 90% power, and a 95% one sided confidence interval around a treatment difference of zero. The identification of women who leave and do not leave the pool prior to delivery of the placenta can only be captured by addition of new data items in the prospective cohort. As delivery of placenta in water, or postpartum haemorrhage of >1,000 ml following waterbirth are relatively uncommon events (17% and 1% respectively) the proposed sample size of 30,000 women who use a birth pool will be underpowered to detect a difference in these outcomes, but will be described.

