#### 15.3 Sensitivity analysis

For both primary outcomes a number of sensitivity analyses will be performed to assess the robustness of the results to factors which may introduce bias.

Propensity score analysis: whether a woman who uses water immersion during labour remains in the pool for birth is likely to be influenced by their age, parity and other characteristics. This will result in imbalanced comparison groups. Incorporating propensity scores, i.e. the 'propensity' of a woman to choose a waterbirth, in the analysis is a way of controlling for this bias. It also allows a more detailed examination of the impact of imbalanced comparison groups on the results. Differences in baseline characteristics before and after propensity score matching will be examined and analyses re-run.

Instrumental variable analysis: Instrumental variables (IV) are factors associated with outcomes only via their association with exposure (in this case to birthing in water) and are independent of other factors associated with exposure. IVs can deal with the unobserved factors in selection bias and can add potential value to a study dealing with just observable factors. Such variables might include midwifery practice, or other factor that encapsulates unit culture. The capture of denominator data to provide information on the proportion of women using water for labour or birth at each unit, and the qualitative component of the study, will be utilised in this analysis.

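### The 90% power in 9.6.1 belongs to an unadjusted risk difference, not to the covariate-adjusted logistic model that 9.6.5 makes the main analysis

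*Protocol*

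**What the plan says.** Protocol 9.6.1 takes OASIS rates from an earlier national cohort, "overall 4.6% and 1.6% of nulliparous and parous women respectively, sustained OASIS", and sets margins of 1.0 and 0.6 percentage points. It concludes: "A sample size of 15,000 nulliparous and 15,000 parous 'low risk' women (7,500 each water and land) is required to obtain 90% power". The criterion is "a 95% one-sided confidence interval around a treatment difference of zero". The neonatal composite is handled in the same way, with a 5% rate and a 1.0-point margin: "16,200 babies (8,100 per group water / land) are required to have 90% power". No covariate or imbalance term appears.

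Protocol 9.6.5 fits an unadjusted logistic model first. It then says "Adjusting for potential confounders may result in a more precise treatment effect estimate", describes choosing covariates with causal diagrams, and continues: "The main logistic model will incorporate these selected covariates through regression adjustment". The 90% intervals are calculated for the odds ratio. The decision rule is worded as an upper limit for a difference, with an odds-ratio equivalent in brackets (1.23 nulliparous, 1.38 parous, 1.21 neonatal).

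Protocol 15.3 expects age, parity and other characteristics to influence who stays in the pool: "This will result in imbalanced comparison groups".

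**The concern.** The power figure and the deciding analysis do not match. Power is stated for two unadjusted proportions compared on the difference scale. The main model is adjusted and logistic, with odds ratios as output. The only remark on how adjustment affects precision points the wrong way for that output.

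The study rests on three non-inferiority conclusions, each presented at 90% power. If an adjusted comparison failed to show non-inferiority, it would be read as the result of a 90%-power test. The unadjusted comparison sits closer to the stated power but is exposed to the confounding that the protocol itself expects.

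**Working it through.** **Inputs.** From 9.6.1: one-sided 5%, 90% power, true difference zero, equal groups, and the rates, margins and sizes above. From 9.6.5: odds-ratio limits 1.23, 1.38 and 1.21. Assumed: R² of waterbirth on the model covariates, which the protocol does not give, at 0.05, 0.10 and 0.20.

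**1. The stated sizes.** n per group = (1.6449 + 1.2816)² × 2p(1−p)/margin², where the squared term is 8.564.

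- Nulliparous: 8.564 × 2 × 0.046 × 0.954 / 0.010² = 7,517 (stated 7,500)
- Parous: 8.564 × 2 × 0.016 × 0.984 / 0.006² = 7,491 (stated 7,500)
- Neonatal: 8.564 × 2 × 0.05 × 0.95 / 0.010² = 8,136 (stated 8,100)

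Power at the stated sizes is Φ(margin/√(2p(1−p)/n) − 1.645) = 89.9, 90.0 and 89.9%. So the 90% reproduces with no covariates, on the difference scale.

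**2. The odds-ratio limits.** Converting p + margin against p gives 1.230, 1.383 and 1.213, which agrees with 9.6.5.

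**3. Unadjusted power against those limits.** SE of the log odds ratio = √(2/(n p(1−p))) = 0.0780, 0.1301 and 0.0721. Power = Φ(ln(limit)/SE − 1.645) = 84.4, 79.7 and 84.1%. The shortfall arises because the margin is a shorter distance on the log scale. For nulliparous women ln 1.23 = 0.207, whereas the linear equivalent of the difference-scale calculation is 0.010/(0.046 × 0.954) = 0.228.

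**4. What adjustment does to the log odds ratio.** Over 100,000 random settings of a binary covariate, the large-sample variance ratio (adjusted to unadjusted) never fell below 1 (minimum 1.000002). In simulated logistic fits (300 per setting, true odds ratio 1, nulliparous figures):

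| R² | Unadjusted SE | Adjusted SE | Ratio | √(1/(1−R²)) |
|---|---|---|---|---|
| 0 | 0.0781 | 0.0786 | 1.006 | 1.000 |
| 0.083 | 0.0786 | 0.0824 | 1.048 | 1.044 |
| 0.20 | 0.0790 | 0.0883 | 1.118 | 1.118 |

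So 1/(1−R²) is a good approximation here. At R² = 0.20 the unadjusted log odds ratio averaged −0.49 against a true value of 0, and the adjusted one 0.005. Adjustment is needed for bias.

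**5. What it does to a risk difference standardised from the same model.** For a binary covariate with outcome risks of 2% and 8%, equal groups, and prevalences centred on 50%, R² is the squared prevalence difference.

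| Prevalence | R² | Variance ratio | 1/(1−R²) |
|---|---|---|---|
| 45% v 55% | 0.01 | 0.991 | 1.010 |
| 40% v 60% | 0.04 | 1.023 | 1.042 |
| 30% v 70% | 0.16 | 1.17 | 1.19 |

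On this scale mild imbalance can leave a slight gain, and 1/(1−R²) somewhat overstates the loss.

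**6. Power at the planned sizes, with variance multiplied by 1/(1−R²)** (nulliparous / parous / neonatal, %):

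| R² | Difference scale | Odds-ratio limits |
|---|---|---|
| 0 | 89.9 / 90.0 / 89.9 | 84.4 / 79.7 / 84.1 |
| 0.05 | 88.6 / 88.7 / 88.5 | 82.7 / 77.9 / 82.4 |
| 0.10 | 87.0 / 87.1 / 87.0 | 80.9 / 75.9 / 80.6 |
| 0.20 | 83.4 / 83.5 / 83.3 | 76.7 / 71.5 / 76.4 |

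**The case against.** The precision remark is hedged, and no reduction in sample size was taken on the strength of it. The text around it already speaks of confounders and bias. This is fair: deleting that sentence alone would change no model, margin or decision.

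The size of the loss rests on an R² that the protocol does not supply. At 0.05 the loss is under 1.5 points on the difference scale. Parity, one of the two drivers of imbalance that 15.3 names, does not enter R² for any of the three conclusions: OASIS is judged within parity strata, and Table 1 does not mark parity for the neonatal outcome. This stands, so the figures are a range and not an estimate.

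The 7,500 is set by the scarcest group, nulliparous waterbirths, and 9.6.1 expects the other three maternal groups to be more prevalent. With 7,500 nulliparous waterbirths, 9,375 land births would offset R² = 0.10, because 1/7,500 + 1/9,375 is 0.9 × 2/7,500. These counts are illustrative, since the protocol gives none, and it claims no such surplus for the neonatal outcome.

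A reader might go further and infer that adjustment can only cost precision, that the loss is the same on any scale, or that the study will certainly have less than 90% power. The protocol does not support these readings. Step 5 shows a possible gain for a standardised risk difference. Step 3 shows that scale matters before any adjustment. The maternal groups may also exceed the planned sizes.

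**Conclusion.** The point holds in a limited form. The stated 90% is the power of an unadjusted risk-difference comparison. It is not shown for the adjusted logistic model that 9.6.5 makes the main analysis, and at the planned sizes it is not the power of that model's odds ratio. The precision rationale fails for the adjusted odds ratio; the valid reason to adjust is confounding.

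If the decision is made on the difference scale, the cost is modest: roughly 1 to 7 points over the assumed R² range, and possibly nothing under mild imbalance. If it is made against the stated odds-ratio limits, the change of scale costs about 6, 10 and 6 points before adjustment, and R² = 0.10 costs about 3.5 to 4 more. All of this assumes equal groups at the planned sizes, a true effect of zero, and the 1/(1−R²) approximation.

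**What to change.** In 9.6.5, say that adjustment is made to control confounding and drop the suggestion that it may sharpen the estimate. In 9.6.1, restate the power of the adjusted main model on the scale actually used for the non-inferiority decision. A correction of n to n(1−R²) on the difference formula alone would miss the larger gap if the odds-ratio limits decide.

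Take R² from a regression of waterbirth on the available Table 1 covariates within parity strata, using no outcomes. Section 9.6.1 already plans to examine the retrospective extract for the parity ratio, so this can be done at the same point. Section 5.4 lists the reason for leaving the pool as a newly added item, so the retrospective R² should be treated as provisional for a comparison group limited to women who left without clinical need. Use the actual group sizes, because the land and parous groups may exceed 7,500.

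The cost is wording in two sections, one regression, and a somewhat less favourable stated power. No extra women are needed.
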